24b. If blinded, how blinding will be achieved and description of the similarity of interventions

N/A

24c. If blinded, circumstances under which unblinding is permissible, and procedure for revealing a participant's allocated intervention during the trial

N/A

Methods: Data collection, management, and analysis

25. Data collection methods

25a. Plans for assessment and collection of trial data

The study will be conducted in partnership with a private school in Bangalore, India in which instruction is provided in English. Participation in the study will be under supervision across five class periods. Participants will complete all survey measures online. A lump-sum payment will be made to the school partner to provide support for students in the school.

All data will be collected in electronic form, via direct entry into Qualtrics or the chatbot from the school's computer lab.

Data to be collected are summarized in Section 16 (Outcomes) as well as Appendix E (List of Measures). The forms used for data collection are available on request from the first author.

25b. Plans to promote participant retention and complete follow-up

Because the study is conducted within a school setting during regular class hours, participant retention is expected to be very high.

26. Data management

Every effort will be made to ensure data security. Survey data will be input directly into Qualtrics. Interactions with the AI chatbot will be hosted, logged and stored on Digital Ocean servers certified under SOC 2 Type II and ISO 27001 standards. OpenAI GPT-4.1 will be used as a secure and private AI service but will not retain or store any participant data.

Students will be identified by a coded ID in the research dataset. Researchers will provide a list of coded IDs to the partner school. The school will create a table with a unique coded ID for each student's name. The table will be owned by the partner school and deleted after the last survey is administered (7 weeks after intervention).

Only researchers involved in this study will have access to the study datasets. Data may be stored on password-protected personal laptops of study staff.

The project completed a successful Data Safety and Security Review at Harvard University (Safety Submission ID: DAT25-0595).

27. Statistical methods

27a. Statistical methods used to compare groups for primary and secondary outcomes

Statistical models

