For the mediation analysis, we will use structural equation modeling (SEM) in R (lavaan) to test whether change in Growth Mindset mediates the effect of the intervention on change in BFS-Internalizing. The primary model will specify: Intervention \rightarrow Growth Mindset \rightarrow BFS-Internalizing, with baseline levels of both constructs included as covariates. We will use a latent change score (LCS) mediation model or an observed (composite-score) change model. Indirect effects ($a \times b$) will be estimated using bias-corrected bootstrap 95% confidence intervals, and standardized effects will be reported. Missing data will be addressed using Full Information Maximum Likelihood (FIML) or pooled multiple imputation, consistent with the main analysis. Because indirect effects are typically smaller than direct effects, and given the available sample size ($N \approx 430$), we expect adequate power to detect small-to-moderate indirect effects but limited power for very small ones. Accordingly, this mediation analysis is secondary and exploratory, and findings will be interpreted cautiously.

Transformations

We will examine the distribution of each outcome and apply transformations or generalized linear mixed-effects models as appropriate. For example, if data are heavily right-skewed, we may rescale continuous outcomes to a (0,1) range and fit a **beta-distributed model** to better approximate the observed distribution.

Inference criteria

Two-tailed tests ($\alpha = .05$) will be used.

27b. Definition of who will be included in each analysis and in which group

Participants enter the analysis cohort at randomization, which occurs after assent and baseline measures. Assenting students will be excluded if they do not have the opportunity to complete the baseline measures (e.g., due to interruption or absence) or if they later withdraw consent or assent and ask for their data to be excluded; all others will be included.

All planned analyses will be conducted using the full participant sample (intention-to-treat). We will also conduct subgroup analyses among students with elevated baseline internalizing symptoms—defined as scores ≥ 1 SD above the mean—following established norms for youth mental health measures (e.g., Youth Self-Report; Achenbach & Rescorla, 2001). These analyses will explore whether intervention effects differ when the program is used as a universal versus indicated prevention approach.

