27c. How missing data will be handled in the analysis

We will address missing data using **multiple imputation** via the **mice** package in R. Prior to imputation, we will examine patterns of missingness and conduct sensitivity analyses to assess whether data appear to be **missing at random (MAR)** versus systematically missing. Imputation models will include all variables used in the main analyses and relevant auxiliary variables to support the MAR assumption.

Appropriate imputation methods will be specified by variable type (e.g., predictive mean matching for continuous variables, logistic or polytomous regression for categorical data). For bounded or highly skewed variables, we may apply transformations (e.g., logit or log) prior to imputation and back-transform results after pooling. If multilevel dependencies (e.g., students nested within classrooms) substantially affect missingness patterns, we will use multilevel imputation approaches (e.g., miceadds or mitml) to preserve the nested data structure.

The number of imputed datasets will approximately match the percentage of missing data for each outcome (rounded up to the nearest whole number, e.g., three imputations for $\sim 2\text{--}3\%$ missingness). Analyses will be pooled across imputations using **Rubin's rules**, providing **intent-to-treat** estimates that retain power and reduce bias relative to listwise deletion.

Effect sizes (e.g., Cohen's d with 95% confidence intervals) will be derived from model-based estimates using the **effectsize** or **MOTE** packages in R, based on t -values from treatment effects in the pooled analyses.

27d. Methods for any additional analyses (e.g., subgroup and sensitivity analyses)

1) We will conduct exploratory qualitative analyses of participants' growth mindset reflections using AI-based text analysis tools, supplemented by manual review where appropriate. In addition to categorizing responses into themes, we will code whether reflections demonstrate (a) valid understandings of growth mindset, (b) positive applications of growth mindset in real-life contexts, or (c) specific intentions to apply growth mindset principles. We will also explore whether baseline demographic variables are associated with the presence or absence of these codes.

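### Section 27c ties the number of imputations to the percent missing with no minimum: at 1% missing or less Rubin's rules cannot be applied, and at m = 3 a borderline p-value depends on the seed

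*Combined protocol and SAP*

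**What the plan says.** Section 27c handles missing data by multiple imputation: "We will address missing data using multiple imputation via the mice package in R". On the number of imputations it says "The number of imputed datasets will approximately match the percentage of missing data for each outcome", with the qualifier "rounded up to the nearest whole number, e.g., three imputations for" about 2-3% missing. It then requires Rubin's rules: "Analyses will be pooled across imputations using Rubin's rules". Effect sizes and their confidence intervals are derived from the same pooled results, "based on t -values from treatment effects in the pooled analyses".

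Two other places bear on how much will be missing. Section 25b says that "participant retention is expected to be very high", without a percentage. Section 27b keeps baseline nearly complete by design: "Assenting students will be excluded if they do not have the opportunity to complete the baseline measures".

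The plan gives no minimum m, no random seed and no check of Monte Carlo error. It does not say whether the percent missing is counted per wave or over all three waves. FIML is offered as an alternative for the mediation model only (Section 27a).

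**The concern.** A rule that links m to the percent missing gives its smallest values when little is missing, and little missing is what the plan hopes for. Two things follow.

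- At the bottom of the range, rounding up returns m = 1. Rubin's rules need at least two imputed data sets to estimate the between-imputation variance, so the stated analysis cannot be carried out.
- At m = 3, the pooled estimate carries avoidable random noise from the imputation draws. With no seed fixed in advance, a primary result close to .05 could fall on either side depending on an undocumented choice. Section 24a says that researchers are not blinded, which makes it more useful to settle that choice beforehand.

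**Working it through.** **Inputs from the plan.** m is the percent missing, rounded up, with m = 3 at about 2-3% (27c). Pooling is by Rubin's rules (27c). Tests are two-sided at .05 (27a). N is about 430, allocated 1:1 (19, 21b).

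**Assumptions not in the plan.** FMI is roughly equal to the percent missing; 1% to 4.5% is shown. The simulation check also assumes a between-wave correlation of 0.6 and missingness at the two follow-ups only.

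**1. The plan's own figure.** Rounding up 2.5% or 3.0% gives m = 3, so the example is reproduced.

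**2. The low end.** Rounding up 0.2%, 0.5%, 0.9% or 1.0% gives m = 1 each time. Rubin's total variance is T = W + (1 + 1/m)B, with B = sum of (Q_i - Qbar)^2 / (m - 1). At m = 1 this B is 0/0, so T, the t-value and the degrees of freedom do not exist. The counts needed are:
- per wave: 4/430 = 0.93% gives m = 1, while 5/430 = 1.16% gives m = 2;
- over three waves with baseline complete: 6 missing at each follow-up is 12/1,290 = 0.93%, so m = 1.

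**3. Cost of ignoring B at m = 1.** With total variance scaled so that W = 1 - FMI and B = FMI, the correct variance is W + 2B = 1 + FMI and the variance used would be 1 - FMI. At FMI = 1% the SE ratio is sqrt(0.99/1.01) = 0.990. The test would reject at 1.96 x 0.990 = 1.941, a type I error of about .052.

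**4. Stability of the SE at m = 3, FMI = 3%.** The coefficient of variation of the SE is about FMI / sqrt(2(m - 1)) = 0.03/2 = 1.5%. Degrees of freedom are (m - 1)/FMI^2 = 2/0.0009, about 2,200. Both are stable. At m = 2 they are about 2.1% and 1,100.

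**5. Noise in the point estimate.** Its SD between seeds, in units of the SE, is sqrt(FMI/m). For a result with large-m p = .05, 95% of seeds give z within 1.96 +/- 1.96 x that SD.

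| FMI | m | SD / SE | p for 95% of seeds |
|---|---|---|---|
| 2% | 3 | 0.082 | .034-.072 |
| 3% | 3 | 0.100 | .031-.078 |
| 4.5% | 3 | 0.122 | .028-.085 |
| 3% | 20 | 0.039 | .042-.060 |
| 3% | 50 | 0.024 | .045-.056 |
| 3% | 100 | 0.017 | .046-.054 |

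For FMI 3% and m = 3: 1.96 - 0.196 = 1.764 gives p = .078, and 1.96 + 0.196 = 2.156 gives p = .031. The 4.5% row is included because baseline is nearly complete, so FMI for a week-7 contrast can exceed the percent missing over all waves.

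**6. Simulation check.** With 430 students, three waves and a random-intercept week-7 contrast, the range at m = 3 was .034-.076 at FMI 2.1% and .032-.085 at FMI 3.3%. At FMI 3.3% it was .042-.060 for m = 20 and .045-.056 for m = 50. These agree with the formula.

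**7. A single case.** A result with large-m p = .04 has z = 2.054, which is 0.094 above 1.96. At m = 3 and FMI 3% that is 0.94 SDs, so about 17% of seeds would give p above .05. At m = 50 it is 0.094/0.0245 = 3.8 SDs, below 0.1%.

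**The case against.** Much of the case on the other side stands.

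- **m = 1 is not shown to be the expected case.** The only missingness figure in the plan is the illustrative 2-3%, and very high retention is not quantified. Each follow-up is a single scheduled class, students may decline to answer (Section 17), and absence is foreseen even at baseline (27b). A reader might infer that the analysis is headed for m = 1; the documents support only that it could happen. At exactly 0% no imputation is needed.
- **Standard errors are not unstable at m = 2 or 3.** A reader might infer this because B then rests on one or two degrees of freedom. At 3% FMI, however, B is only about 3% of the total variance, and step 4 shows that the pooled SE hardly moves. The noise is in the point estimate.
- **The noise is not peculiar to small m.** Whenever m = 100 x FMI, the SD is 0.10 SE: m = 3 at 3% is no noisier than m = 30 at 30%.
- **The test stays valid.** The (1 + 1/m)B term already counts this noise. The added variance is FMI/m = 0.03/3 = 1%, or about 0.5% on the SE, which costs roughly 0.4 points of power at 80%.
- **A different m per outcome biases nothing that can be shown.** The imputation models are to include all analysis variables, and FIML is available for the mediation model, which uses two outcomes jointly.

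One argument does not stand. It could be said that the word approximately lets the analyst use two or more imputations. The rounding instruction and the worked example fix the reading, and neither supplies a floor.

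**Conclusion.** The point holds, at low severity. The rule is wrong as written for missingness above 0% and up to 1%, because the required pooling then cannot be computed. The practical damage there would be small (type I error about .052 at an FMI of 1%).

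Elsewhere the rule works but leaves avoidable noise. In the plan's own example the estimate moves by about 0.10 SE between seeds, so significance can turn on the seed when p is about .03-.08. This rests on FMI being close to the percent missing, and the .031-.078 range is a 95% range for a result sitting exactly at p = .05. A result well away from .05 is not affected. The documents do not support reading this as an invalid primary test or as bias between outcomes.

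**What to change.** In Section 27c, replace the percentage rule with one fixed m for all outcomes. At least 20 removes the m = 1 failure and narrows the range to about .042-.060 at 3% FMI; 50 narrows it to about .045-.056. State the random seed in advance. For convenience, run all models from one common imputed data set, which also settles which imputations the mediation model uses if it is not fitted by FIML. The change is a sentence or two of text and minutes of computing. It does not touch participants or trial conduct, and Section 31 already provides for updating the document and the registry.

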Appendix A: Study Procedures

Advance Preparation: Parental Consent and Roster

Roster: The school will create and maintain a “study roster” for students. The roster will contain three columns: student name, coded ID, and whether the student has opted out of the study (or has been opted out by their parent/guardian) for any reason. Researchers will provide the school with a set of valid coded IDs (4 digits each) and the school will assign them to students. To protect the identity of participants, the mapping from student name to coded ID will be owned by the school and will be deleted when the study concludes.

Parental consent: The school principal will contact at least one legal guardian of all eligible students (grades 6-8) to provide an overview of the study and explain the process of passive consent. This outreach will take place via an electronic system. We will use passive, opt-out consent in which parents/guardians have 2.5 weeks to opt out a student from the study. If a guardian opts their child out of the study, this information will be recorded in the study roster and the child will not be invited to participate.

Class 1: Student Assent and Baseline Measures

During the period scheduled for technology class, all students will report to the school computer lab as per usual. Each student will access a personal, Internet-connected computer.

The technology teacher will read an informational “Script” to orient students to the study. A researcher will be available on a video call to answer any questions students might have. In addition, at least one local assistant (recruited by the study team) will be physically present in the class to help with the procedures.

The teacher will visit each student in the class, carrying the study roster. A preloaded webpage on each student’s computer will be used to enter the student’s coded ID, or to click “opt out” if a parent has already opted out for the student.

- Students whose parents have opted out will do an alternate classroom activity.
- Students who might participate will automatically be redirected to a digital assent form.
- Any students who decline to participate will do an alternate classroom activity.
- Students who agree to participate will proceed to answer brief survey questions (Demographics, Behavior and Feelings Survey – Internalizing Subscale, Growth Mindset Scale)

The process above might not require the full class period. Any students who finish early will do an alternative activity assigned by the teacher.

After class, researchers will randomly assign assenting students to control and intervention groups. They will create a table that maps each student’s coded ID to one of three cases: control, intervention, or opt out. This information will be provided to the school to merge with the study roster.

Classes 2 and 3: Growth Mindset Training for Intervention Group

In the next two scheduled periods of technology class, students will be divided into two groups. Students in the intervention group will sit on one side of the computer lab, while students in the control group (and any students who have opted out) will sit on the other side.

Students in the intervention group will do the training program by interacting with an AI chatbot. On the second day of the intervention, following the intervention (or if time runs out, during the last 5 minutes of the class period), students will complete a brief survey to provide program feedback.

Students in the control group (and anyone who opted out) will complete an alternate activity identified by the technology teacher (e.g., a learning activity on the computer). This activity will not take the form of a graded assignment but will be an additional enrichment activity.

Class 4: Follow-up Survey

Three weeks after the training, all participants will be asked to complete a brief follow-up survey (approximately 10 minutes). This activity will occur at the beginning of a normal technology class. As before, the teacher will assist students in entering their coded IDs. Students who have opted out will do an alternate activity.

Class 5: Follow-up Survey and Growth Mindset Training for Control Group

Seven weeks after the training, all participants will be asked to complete a brief follow-up survey (approximately 10 minutes). This activity will occur at the beginning of a normal technology class. As before, the teacher will assist students in entering their coded IDs. Students who have opted out will do an alternate activity.

After the survey, the control group will complete a shortened (15 minute) version of the growth mindset training while the intervention group and opted-out students will do an alternate activity.

Following this class, a printed booklet with all the content from the full version of the training will be provided to all students in grades 6-8.

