We will conduct a parallel group randomized controlled trial with simple individual randomization (1:1) of participants to control and intervention groups. During the intervention, the control group will engage in quiet classroom activities assigned by the teacher. After 7 weeks, the control group will receive a shortened version of the intervention (while the intervention group engages in alternate classroom activities).

Methods: Participants, interventions, and outcomes

13. Trial setting

The trial will take place in our partner school (a single site). The school is a private school in urban Bangalore and conducts classes in English. It caters to students from diverse backgrounds from Grade 1 to Grade 12.

14. Eligibility criteria

14a. Eligibility criteria for participants

Inclusion criteria:

- (i) Youth in grades 6-8 at our partner school.
- (ii) Youth assents to participate and a parent/guardian provides passive consent (does not opt-out of participation)

Exclusion criteria:

- N/A

14b. If applicable, eligibility criteria for sites and for individuals who will deliver the interventions)

N/A

15. Intervention and comparator

15a. Intervention and comparator

Participants will interact with an AI chatbot for approximately 45 minutes (split across two class periods). The tutorial has a structured script and pauses at section boundaries to allow for brief interactions. It also contains culturally grounded comics and illustrations with role-playing scenarios to engage with students.

Example interactions with the AI chatbot, including open-source code needed to reproduce it, will be made available at <https://github.com/[name]/growth-mindset-chatbot>

The comparator (alternate classroom activities) will be assigned by the teacher. The specific activities that students engage in will be noted and reported with the results of the trial.

15b. Criteria for discontinuing or modifying allocated intervention/comparator for a trial participant

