		X			X	X
				X		
					X	X
Growth mindset reflections (intervention group)						

19. Sample size

Our sample size is constrained by the number of available students in the school. We expect about 450 students to be invited to participate (150/students per grade across 3 grades). Assuming an opt-out rate of 5%, we can expect a sample size of about 430 students.

For our primary tests of intervention effects (i.e., mixed effects model examining the time [baseline, 3-week FU, 7-week FU] * condition [Intervention or Control] interaction), an a priori power analysis shows that our sample size can detect effects as small as 0.22 (using two-tailed tests with $\alpha = .05$, $\beta = 0.2$). This effect size is comparable to that detected by a prior single-session growth mindset intervention (Schleider & Weisz, 2018).

20. Recruitment

All students in grades 6-8 at our partner school will be invited to participate.

The school partner was based on strong pre-existing relationships with the research team. The decision to focus on grades 6-8 was made in consultation with the school principal, who believed that these grades would benefit from the intervention while also having flexibility in their curriculum.

Methods: Assignment of interventions

21. Randomization: Sequence generation

21a. Who will generate the random allocation sequence and the method used

The first author will perform the randomization using R.

21b. Type of randomization (simple or restricted) and details of any factors for stratification.

Simple individual randomization (1:1) of participants to intervention or control group.

22. Allocation concealment mechanism

The use of central randomization will ensure that students and teachers cannot determine trial allocation ahead of time. Allocation to the experimental or control groups will take place when class is not in session (between the day of enrollment and the start of the intervention.)

23. Implementation of randomization

As the study procedures are conducted online, assignment of participants to intervention or control groups is done electronically and not by any personnel. Hence no personnel can influence the implementation of the randomized assignment.

24. Blinding

24a. Who will be blinded after assignment to interventions (e.g., participants, care providers, outcome assessors, data analysts)

The intervention will be unblinded for teachers, students and researchers.

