All statistical analyses will be performed using R. To evaluate intervention effects, we will use a series of mixed-effects regression models implemented via the lme4 package (or comparable tools). Each model will include Time (baseline, 3-week, 7-week), Condition (intervention vs. control), and their interaction (Condition \times Time) as fixed effects, with random intercepts for participants and, where feasible, classroom to account for nesting. The Condition \times Time interaction will test whether outcome trajectories differ between groups over time.

If outcome distributions deviate substantially from normality, we may use generalized linear mixed-effects models with an appropriate link function (e.g., logit, log, or beta) or apply suitable transformations (e.g., rescaling data to a (0,1) interval for beta regression) to improve model fit. All models will be checked for assumptions, including residual distribution and heteroskedasticity.

We will calculate both within-subject and between-subject effect sizes for intervention effects on continuous outcomes. For mixed-effects models, standardized mean differences will be computed from estimated marginal means and pooled residual variance (e.g., using effectsize::t_to_d() or contrasts via emmeans). All effect sizes will include 95% confidence intervals and, when available, Common Language (CL) effect sizes to facilitate interpretation.

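### Baseline BFS is recorded before a simple randomization, and the primary model does not adjust for it: a loss of precision, not a bias, that a change to Section 27a recovers

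*Combined protocol and SAP*

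**What the plan says.** **Allocation.** Section 12 describes "simple individual randomization (1:1) of participants to control and intervention groups". Section 21b, where stratification factors would be listed, gives only "Simple individual randomization (1:1) of participants to intervention or control group".

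**Timing.** Section 27b states "Participants enter the analysis cohort at randomization, which occurs after assent and baseline measures". Section 22 places allocation "between the day of enrollment and the start of the intervention", and Appendix A (Class 1) says "After class, researchers will randomly assign assenting students to control and intervention groups". Baseline BFS, the primary outcome measure, is therefore on file for every student who is assigned.

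**Analysis.** Section 27a fits Time (three levels, baseline included), Condition and their interaction, with "random intercepts for participants and, where feasible, classroom to account for nesting". The interaction is the test of the intervention. Baseline levels appear as covariates only in the mediation model of the same section.

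**Class identity.** Appendix A says of the school's file: "The roster will contain three columns: student name, coded ID, and whether the student has opted out of the study". Appendix E asks students for their grade, not their class.

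**The concern.** The usual reason for simple randomization is that the next assignment cannot be guessed. That reason carries little weight here, because students are assigned in a batch after enrollment, and the documents give no other. The baseline value of the primary outcome is available and used neither in the allocation nor as a covariate in the primary model.

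In a difference-in-change analysis a chance baseline gap is subtracted in full, although only part of it (the within-student correlation) would have persisted to follow-up. The excess is noise in the treatment contrast. The classroom random intercept does not help, since a constant class effect cancels from each student's change.

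Section 19 says that the size of the school limits the sample, so precision has to come from design or analysis. What is at stake is power on the first primary outcome.

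**Working it through.** **Inputs from the documents (Section 19).** "we can expect a sample size of about 430 students" (450 x 0.95 = 427.5), so about 215 per arm; two-sided alpha 0.05; power 0.80; smallest detectable effect 0.22, metric not stated and taken here as SD units.

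**Assumptions not in the documents.** Within-student correlation rho = 0.6 (range 0.5 to 0.7), equal variances, 12 classes, class-by-wave variance 2% of the total, elevated subsample 16% of students.

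**1. The plan's 0.22.** With 1.960 + 0.8416 = 2.8016 and sqrt(4/430) = 0.0964, a comparison that ignores correlation detects 2.8016 x 0.0964 = 0.270. Reaching 0.22 needs a variance factor of (0.22/0.270)^2 = 0.663. For change to one follow-up the factor is 2(1 - rho), which needs rho of about 0.67. For change to the mean of both follow-ups it is 1.5(1 - rho), which needs rho of about 0.56. So 0.22 is attainable but cannot be confirmed from the text.

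**2. Chance baseline gap.** The gap has SD 0.0964.
- P(at least 0.10 SD) = 2[1 - Phi(0.10/0.0964)] = 30%
- P(at least 0.11 SD, half of 0.22) = 25%
- P(at least 0.22 SD) = 2.2%

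**3. What reaches the contrast.** Given a gap g, the expected shift in the change contrast is -(1 - rho) x g. For g = 0.11 that is -0.055, -0.044 and -0.033 at rho 0.5, 0.6 and 0.7; simulation gave -0.051, -0.040 and -0.034. In the same runs (6,000 trials per setting, mean of both follow-ups, class ICC 0.03), overall type I error was 4.9% to 5.2%. Among trials with a gap of at least 0.10 SD it was 9% to 11%, against 4.5% to 5.4% with baseline as a covariate.

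**4. Precision, baseline to one follow-up.** As planned, SD = sqrt[(4/430) x 2(1 - rho)]. Adjusted, SD = sqrt[(4/430) x (1 - rho^2)]. The variance ratio is (1 + rho)/2. Detectable effect = 2.8016 x SD.

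| rho | SD planned | SD adjusted | Variance ratio | Detectable, planned | Detectable, adjusted |
|---|---|---|---|---|---|
| 0.5 | 0.096 | 0.084 | 0.75 | 0.27 | 0.23 |
| 0.6 | 0.086 | 0.077 | 0.80 | 0.24 | 0.22 |
| 0.7 | 0.075 | 0.069 | 0.85 | 0.21 | 0.19 |

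At rho 0.6, power for an effect of 0.22 is Phi(0.22/0.0863 - 1.96) = 72% as planned and Phi(0.22/0.0772 - 1.96) = 81% adjusted.

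**5. Design against analysis.** Simulated SD of the same contrast at rho 0.6, with 12 classes and 2% class-by-wave variance:
- simple randomization, planned change model: about 0.085 to 0.086
- simple randomization, baseline covariate plus class effects at follow-up: 0.0765
- BFS-ranked pairs within class, planned change model: 0.0759
- BFS-ranked pairs within class, same adjustment: 0.0756

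Taking 0.0862 for the first, adjustment alone recovers (0.0862 - 0.0765)/(0.0862 - 0.0759) = 94% of the pairing gain. Pairing on top of adjustment adds (0.0765 - 0.0756)/0.0765, about 1%. Balancing on class alone gives sqrt[(4/430) x 2 x 0.38] = 0.084. Under pairing, the planned model still reports a standard error of about 0.086, so most of the gain never reaches the test: power moves only from 72.7% to 75.0%.

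**6. Elevated subsample.** 0.16 x 430 is about 68 students. The 95% binomial range in one arm is 26 to 42. At 26:42 the variance factor is (1/26 + 1/42)/(2/34) = 1.059; at 29:39 it is 1.022.

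**The case against.** The strongest reply is that simple randomization of about 430 students is valid and standard. Chance imbalance is already inside the standard error, and overall type I error stays near 5%. The 12 classes and the 2% class-by-wave variance are assumed, and with no class-by-wave variance balancing on class alone gains nothing. All of that stands. It answers a charge of bias; it does not explain why the primary model leaves baseline unadjusted.

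A reader might infer more than the documents support:

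- **That the trial is biased, or that a gap can swallow half the effect sought.** Section 19 gives 0.22 as the smallest detectable effect, not as a target, and only about (1 - rho) of a baseline gap enters the contrast.
- **That only balancing arms within class removes class-by-wave noise.** Class-by-time terms in the model remove it too (step 5).
- **That the elevated subsample is compromised by an uneven split.** A 26:42 split costs about 6% in variance. The main limit there is the size of the subsample.
- **That researchers hold class lists.** No section says so. Class might be inferred from the class-by-class sessions, but the roster has no class column.

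Timing also limits a design change. Section 1b plans first enrollment for November 3, 2025, allocation falls within the following week (Sections 18 and 22), and this version is dated December 4, 2025. Allocation may be complete.

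**Conclusion.** The point holds as a loss of precision. Simple randomization and an unadjusted difference in change leave unused a baseline score that is on file before assignment. At rho 0.6 the SD of the baseline-to-one-follow-up contrast is about 0.085 as planned and about 0.076 with baseline and class adjustment, or with BFS-ranked pairing within class. Baseline adjustment alone cuts the variance by 15% to 25% over rho 0.7 to 0.5. These sizes rest on the assumed correlation and equal variances and, for the class terms, on the assumed number of classes and class-by-wave variance. Most of the gain is available from the analysis alone, so the analysis is the place to act.

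**What to change.** **Section 27a (main change).** Estimate the primary effect with baseline adjustment, in one of two forms:

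- Model the 3- and 7-week BFS scores with baseline BFS as a covariate. The effect is then the adjusted difference between arms at each follow-up. The interaction in a model with two follow-ups would test only whether that difference changes between 3 and 7 weeks, so the tested contrast must be restated.
- Keep three outcome times but allow no Condition difference at baseline (constrained-baseline model). The Condition-by-follow-up terms are then the effect. Section 27b supports the constraint, since baseline precedes randomization.

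Include class terms, with class-by-time where class is known. Do not simply add baseline BFS to the existing three-time model: a covariate that is constant within a student cancels from the within-student change and leaves the contrast as it was.

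**Sections 12 and 21b and Appendix A (only if allocation is open and class can be identified).** Replace simple randomization with 1:1 randomization within class, in pairs or blocks ranked by baseline BFS. Ranking within class is more workable than stratifying on elevated status, because a cut-off based on the whole-sample mean and SD is unknown until every class has completed baseline. Keep the adjusted analysis, so that the standard error reflects the design.

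**Cost.** A few lines of R and revised wording, recorded under Section 31 and settled before follow-up scores are analysed. No extra students, visits or measures are needed; the class terms need a class label for each coded ID.
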